H6	UNBLINDING PROCEDURES.....	25
I	DATA HANDLING AND RECORD KEEPING.....	25
I1	CONFIDENTIALITY AND SECURITY	25
I2	TRAINING.....	25
I3	CASE REPORT FORMS AND SOURCE DOCUMENTS.....	26
I4	RECORDS RETENTION	26
J	STUDY MONITORING	26
J1	STUDY MONITORING PLAN.....	26
K	STUDY ADMINISTRATION	26
K1	ORGANIZATION AND PARTICIPATING CENTERS.....	26
K2	FUNDING SOURCE AND CONFLICTS OF INTEREST	26
K3	COMMITTEES.....	27
K4	SUBJECT STIPENDS OR PAYMENTS.....	27
K5	STUDY TIMETABLE.....	27
L	PUBLICATION PLAN.....	27
M	ATTACHMENTS	27
M1	TABLES.....	27
M2	INFORMED CONSENT DOCUMENTS.....	27
M3	PATIENT EDUCATION BROCHURES.....	27
M4	SPECIAL PROCEDURES PROTOCOLS	27
M5	QUESTIONNAIRES OR SURVEYS.....	27
N	REFERENCES.....	28

Introduction

Study Abstract

Approximately 2.5 million Americans currently have advanced critical limb ischemia (CLI) [1]. Patients with diabetes are at increased risk of advanced CLI and resultant complications such as wounds, gangrene, and severe infection. This leads to more than 130,000 extremity amputations in the United States per year [2]. Poor major amputation site healing in patients with CLI and diabetes is associated with surgical site necrosis, dehiscence, and infection. In 40% of these patients, subsequent limb re-amputation or surgical site revision is required with added significant patient morbidity, extended disability, and increased healthcare costs [2, 3].

N-Acetyl-Cysteine (NAC) is a well-known thiol precursor of reduced glutathione [4, 5] and has been in clinical use for over 40 years. It is Food and Drug Administration (FDA) approved as a mucolytic agent. However its current primary clinical use is the treatment of acetaminophen poisoning – which is potentially life saving [6, 7]. Multiple studies and clinical trials have investigated the use of NAC as an antioxidant given its free thiol group and its ability to restore glutathione levels [8-10].

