Recent studies have demonstrated that NAC can blunt tissue oxidative stress and decrease insulin resistance [11, 12]. Preclinical studies in our laboratory have also demonstrated that NAC can augment tissue perfusion and arterial collateral maturation (arteriogenesis) in a novel murine hind limb ischemia – amputation model, as well as alter the phospholipid profile in vascular endothelial cells. Recent clinical trials have repeatedly demonstrated the safe administration of NAC [8-10]. **We therefore hypothesize that perioperative administration of NAC in patients with CLI, with and without diabetes, who are undergoing major lower extremity amputation will improve tissue stump perfusion and alter tissue lipidomics.**

Primary Hypothesis

Our primary hypothesis is that perioperative administration of NAC in patients with CLI, plus or minus diabetes, who are undergoing major lower extremity amputation will improve tissue stump perfusion and alter tissue lipidomics, ultimately reducing amputation associated morbidity with respect to wound breakdown, wound infection, and amputation revision.

Purpose of the Study Protocol

The purpose of this study protocol is to evaluate the safety and potential efficacy of NAC in the setting of peripheral arterial disease as a tissue augmentation agent in patients with CLI undergoing lower limb amputation. This will be a Pilot Clinical trial designed to facilitate a future power calculation for a larger, likely multicenter trial that can evaluate the potential clinical benefit of using NAC to improve healing and perfusion of amputation stumps in diabetic patients.

This study is highly innovative in that it will: i) explore a compelling new modality of therapy in a highly vulnerable, but frequently under-represented clinical trial patient population, and ii) represent the potential use of a low-cost, generic, well-established, and generally very safe pharmacological agent for an important clinical problem. This would otherwise not be pursued by drug pharmaceutical manufacturers due to anticipated low-profit margins from a generic pharmacological agent.

Background

Prior Literature and Studies

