Aside from smoking cessation and physical exercise, there are currently no known effective medical treatments for patients with advanced non-surgically correctable CLI [13, 21]. In addition, the prevalence of amputations resulting from CLI among diabetic patients is disturbingly high [2]. Based on our recent preclinical studies, we are proposing a pilot clinical trial to further explore the potential therapeutic benefits of NAC in healing extremity amputation stumps in the setting of CLI, plus or minus diabetes. These studies are highly innovative in that they: i) explore a compelling new modality of therapy in a highly vulnerable, but frequently under-represented clinical trial patient population, ii) explore a completely novel and not previously reported NAC mechanism of action on phospholipid synthesis and expression, and iii) represent the potential use of a low-cost, generic pharmacological agent, which would otherwise not be pursued by drug pharmaceutical manufacturers due to low-profit margins. In short, this proposal may establish a conceptual infrastructure for future larger clinical trials exploring the use of NAC in patients with CLI and with and without diabetes, and identify a previously unknown novel mechanism of action for NAC.

We believe that previous literature supporting the role of NAC in augmenting compensatory tissue perfusion raises the possibility that this may be an advantageous therapeutic agent to favorably alter the tissue lipidomic profile of diabetic patients receiving NAC. We believe that NAC offers a new treatment strategy for patients with CLI undergoing lower extremity amputation with the intent to improve tissue perfusion, healing, and reduce morbidity and mortality associated with lower limb amputation.

Study Objectives

Primary Aim 1

Determine whether NAC can affect major lower extremity amputation stump perfusion by POD (Post-operative Day) 5

Primary Aim 2

Determine whether NAC can affect major lower extremity stump healing for 30 days following amputation.

Secondary Aim

Determine the effect size in diabetic patients that is necessary to power a larger clinical trial to determine whether NAC treatment can improve tissue perfusion and healing at major lower extremity amputation stumps.

Rationale for the Selection of Outcome Measures

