Upon consent and enrollment in the study, relevant subject information will be relayed to the Barnes Jewish Hospital (BJH) Investigational Pharmacy. Prior to proceeding to the operating room for lower extremity amputation, the patients will be randomized 1:1 by the BJH Investigational Pharmacy to either placebo saline infusion (twice daily) or a standard adult intravenous dose of NAC (1200mg twice daily) for 6 days post-amputation during the usual post-operative inpatient extremity off-loading and stump monitoring period. The pharmacy will maintain blinding, with no member of the investigational team having access to the record until the conclusion of the trial.

Early Withdrawal of Subjects

Patients unable to tolerate the administration of the drug will be withdrawn from the study at any point during their hospitalization and will continue to be monitored until their condition stabilizes. Patients unable to participate in the Post-operative Day 0 Non-invasive Laser Assisted Fluorescence Angiography (LAFA) will be withdrawn from the study at that time point and will not receive the investigational product. Subjects for which continuous IV access is not medically indicated during the 6 day study drug administration period may be withdrawn from the study. Patients unable to participate in follow-up appointments will also be withdrawn from the study.

When and How to Withdraw Subjects

Patients unable to tolerate the administration of the drug will be withdrawn from the study trial at any point during their hospitalization. Patients unable to participate in follow-up appointments will also be withdrawn from the study. They will continue to be monitored for adverse events as inpatients for the duration of their hospitalization. Patients unable to participate in the Post-operative Day 0 Non-invasive Laser Assisted Fluorescence Angiography (LAFA) will be withdrawn from the study at that time point and will not receive the investigational product. No further study follow up will be required.

Data Collection and Follow-up for Withdrawn Subjects

Patient data will be collected up until time of withdrawal from the study and pooled into the collective analysis along with all other patients.

Study Drug

Description

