2. The patient is scanned under an existing non-contrast MRI protocol to obtain blood flow and tissue oxygenation pictures at rest.

3. Each study patient is carefully monitored by a physician, nurse practitioner, physician assistant or nurse for signs and symptoms of allergic reaction or intolerance to this non-invasive procedure until discharge.

Visit 1

Following patient discharge, amputation stumps will be evaluated within 20-50 days during a routine post-operative visit using the same anthropometric parameters (LAFA and TcPO₂ will not be performed at this time point).

Safety and Adverse Events

Safety and Compliance Monitoring

All study patients are inpatients at BJH in St. Louis Missouri and are cared for by appropriately trained nurses on the inpatient wards. Vascular surgery Attending Physicians, Vascular Surgery Fellows, Surgical Residents, and a team of Nurse Practitioners oversee their overall care. Inpatient ward nurses routinely assess patients at least every 4 hours with vital signs, intake and output measurements, pain assessment, nutrition assessments, medication review and administration, etc.

Medical Monitoring

Medical monitoring of the study will be performed by the Principal Investigator. The goal of monitoring this study is to enhance human subject protection and to monitor the quality of the clinical trial data by focusing investigator oversight on the most important aspects of study conduct and reporting. The PI will provide regular oversight to ensure adequate protection of the rights, welfare, and safety of the human subjects and the quality of the clinical trial data.

Definitions of Adverse Events

An adverse event (AE) is defined as any untoward medical occurrence in a subject administered a pharmaceutical product or who has undergone study procedures and which does not necessarily have a causal relationship with this treatment. An AE can therefore be any unintended sign (including an abnormal laboratory finding), symptom, or disease temporally associated with the use of the investigational product, whether or not related to the medicinal (investigational) product.

All AEs will be recorded in the CRF from the time of consent through the 30 days post-operative visit. AEs will be followed to resolution or stabilization.

An abnormality identified during a medical test (e.g., laboratory parameter, vital sign, physical exam) should be defined as an AE only if the abnormality meets one of the following criteria:

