All AEs will be recorded in the CRF from the time of consent through the 30 days post-operative visit however all AEs will be followed to resolution or stabilization.

Study Outcome Measurements and Ascertainment

As described previously, study subjects will undergo evaluations using LAFA, TcP02, and anthropometric measurements.

Statistical Plan

Sample Size Determination and Power

The purpose of this study is to obtain sufficient preliminary data to determine the sample size necessary for a future large definitive clinical trial. For this pilot study, we plan to enroll 25 patients in each group, allowing for a dropout rate of 10% per group.

We emphasize that effect size (the expected difference in primary outcome between the treatment and control groups) should not be determined by the pilot study. Rather it is determined by the minimum clinically important difference. However, the effect size from the pilot give us some ideas about possible achievable difference.

Interim Monitoring and Early Stopping

An interim analysis will be conducted once >30 patients are enrolled in the study. Analysis will focus on determining differences between NAC and control group. Interim analysis will help determine early differences between the study groups and safety profile of study intervention. The investigators may end the study early depending on study findings, safety profile of the data, and/or if data is adequate for a peer-reviewed publication.

Analysis Plan

Data analysis include (1) the partition of variation of outcome measurements into within and between patient components to obtain standard deviation of measurements, intra-class correlation of the measurements, (2) use of appropriate regression model (GEE or mixed effect regression) to compare the outcome measurements between two groups, while accounting for the intra-class correlation. Interpretation of analysis should be made within the context of a pilot study where we have a pre-specified hypothesis but do not have power analysis for testing the hypothesis.

Statistical Methods

One of the main study outcomes (and in the future large study) is the stump perfusion assessment, which is a continuous variable measured three times (D0, D3, and D5) after

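### No rule says how a revision, re-amputation, breakdown or infection before Visit 1 enters the Aim 2 healing outcome, and patients who cannot attend follow-up are withdrawn

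*Combined protocol and SAP*

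**What the plan says.** Under Study Objectives, Primary Aim 2 reads: "Determine whether NAC can affect major lower extremity stump healing for 30 days following amputation". The Primary Hypothesis adds the clinical goal of "reducing amputation associated morbidity with respect to wound breakdown, wound infection, and amputation revision". The Study Abstract gives the background burden: "In 40% of these patients, subsequent limb re-amputation or surgical site revision is required". It attaches no time frame to that figure.

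The outcome section (Study Outcome Measurements and Ascertainment) says only that "study subjects will undergo evaluations using LAFA, TcP02, and anthropometric measurements". The wound is one item in the anthropometric list (Schedule of Measurements, part C). It is assessed on POD 3 and POD 5, each time only if the dressings are off and the patient is still in hospital. After discharge there is one assessment, at 20 to 50 days, "during a routine post-operative visit using the same anthropometric parameters" (Visit 1). Part C mentions a stump healing score, but neither document defines it.

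On non-attendance, Early Withdrawal of Subjects and When and How to Withdraw Subjects both state: "Patients unable to participate in follow-up appointments will also be withdrawn from the study". The section on data from withdrawn subjects keeps data up to withdrawal and pools them with the rest. Missing Outcome Data is marked not applicable in both the protocol and the SAP.

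Three other provisions bear on the point. Adverse events go into the CRF from consent through the 30-day post-operative visit. Data Collection Procedures for Adverse Events tells staff not to ask about specific anticipated events. Screening for Eligibility makes outside records optional, for screening or patient care, and allows a second participation on the same limb.

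**The concern.** For Aim 2, the informative patients are those whose stump fails. They are also the ones for whom a single scheduled look works least well. A stump revised or re-amputated before Visit 1 is no longer the stump that was randomized, and no rule says how to score it. A patient too ill to attend, or in another hospital, meets the withdrawal rule, and nothing in the plan supplies a 30-day healing outcome for that patient.

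Two things are at stake. The first is the between-arm healing comparison, one of two primary aims. The second is the healing failure rate passed to the next trial, since the Sample Size section gives planning that trial as the purpose of this one. The adverse-event record does not close the gap by itself. It depends on spontaneous report or open questions at an examination or evaluation, so it is likely to be thinnest for patients who do not come back. The analysis plan does not draw on it for healing.

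**Working it through.** **The plan's own figure.** The plan enrols 25 per group with a 10% dropout allowance: 25 × 0.90 = 22.5 evaluable. A target of 22 evaluable fits (22 / 0.90 = 24.4, rounded up to 25), but no target, power or effect size is given, so the size cannot be derived further. The point does not depend on it.

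**Number of patients concerned.** At the Abstract's 40%, 25 × 0.40 = 10 per arm would need revision or re-amputation. Because 40% has no time frame, take 10% by Visit 1 as an assumed low value: 25 × 0.10 = 2.5 per arm.

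**Timing.** If discharge is on POD 5, and the 20 to 50 days run from discharge, Visit 1 falls on POD 25 to 55. That does not line up with a 30-day aim, so a fixed day is needed before any failure rule can work.

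**Effect on the comparison.** Let p be the true failure rate by the visit and f the share of failures that are revised, or leave the patient unable to attend, before the visit. The documents do not say what happens to these patients, so two cases are shown:
- lost from the analysis: observed rate = p(1 − f) / (1 − pf)
- rescored as healed: observed rate = p(1 − f)

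Assumptions: 40% on placebo (the Abstract's figure, assumed to apply by Visit 1) and 20% on NAC (not in the documents), then a lower pair of 10% and 5%. The share f is the same in both arms.

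| True rates | f | Lost | Rescored |
|---|---|---|---|
| 40% vs 20% (20 points) | 0.25 | 33.3% vs 15.8% = 17.5 | 30% vs 15% = 15 |
| 40% vs 20% (20 points) | 0.50 | 25.0% vs 11.1% = 13.9 | 20% vs 10% = 10 |
| 40% vs 20% (20 points) | 0.75 | 14.3% vs 5.9% = 8.4 | 10% vs 5% = 5 |
| 10% vs 5% (5 points) | 0.50 | 5.3% vs 2.6% = 2.7 | 5% vs 2.5% = 2.5 |

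For example, 40% with f = 0.50 and patients lost: 0.40 × 0.50 / (1 − 0.40 × 0.50) = 0.20 / 0.80 = 25.0%. In that case 0.40 × 0.50 = 20% of placebo patients have no outcome, twice the 10% allowance.

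**Unequal shares.** With rescoring, f = 0.25 on placebo and 0.75 on NAC gives 0.40 × 0.75 = 30% vs 0.20 × 0.25 = 5%, a difference of 25 points, above the true 20. Reversing the shares gives 0.40 × 0.25 = 10% vs 0.20 × 0.75 = 15%, so the sign changes.

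**Effect on planning.** Sizing a two-arm trial on these rates (two-sided 0.05, 80% power) gives 82 per arm at 40% vs 20%, 120 per arm at 25.0% vs 11.1%, and 199 per arm at 20% vs 10%.

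**The case against.** The strongest reply is that the events are not lost. Adverse events are recorded through the 30-day visit and followed to resolution or stabilization. A revision that needs hospitalization would be serious, and POD 3 and POD 5 assessments made before withdrawal are kept. This stands. A reader might infer that failures disappear from the trial, and the documents do not support that. What they lack is a link from the adverse-event record to Aim 2.

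A reader might also infer that a revised stump will be scored on its new wound and counted as healed. The documents do not say so. The healing score is undefined and the wound form is not included, so rescoring is one possible outcome of silence. Nor do the withdrawal sections mention death, so treating a death as a withdrawal would be an interpretation.

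Nor is the direction of bias fixed: the difference shrinks only if the affected share is similar in both arms. The 40% appears in a passage on patients with CLI and diabetes, whereas the trial also takes patients without diabetes.

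Finally, this is a pilot. At 40% vs 20% with 25 per arm, the standard error of the difference is √(0.24/25 + 0.16/25) = 12.6 points. The distortions shown for a quarter or a half of failures affected (2.5 to 10 points) are smaller than that. The plan says it has no power analysis and that the effect size for the next trial should come from the minimum clinically important difference. The hypothesis puts the morbidity events behind the word ultimately. All this limits what the pilot can conclude about efficacy. It does not excuse a biased failure rate, because the plan lists outcome levels with and without treatment among the data the next trial needs.

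**Conclusion.** The concern holds as a gap in outcome definition and follow-up. One primary aim is healing over 30 days. Its only post-discharge assessment is a single visit, the stated rule withdraws those who cannot attend, no missing-data rule exists, and no text brings an earlier failure of the index stump into the outcome. The withdrawal rule makes this more than missing detail, because following it can remove the healing outcome of patients likely to have failed.

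The size is uncertain. With half of failures affected equally in both arms, the difference falls from 20 points to 13.9 or 10, or from 5 points to about 2.7 or 2.5. These figures rest on the assumed NAC rates, the assumed affected share, and a placebo rate that is either the Abstract's undated 40% or an assumed 10%. With unequal shares the difference can grow, shrink or reverse. The change should be made because the remedy is cheap and the healing data are meant to be reused.

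**What to change.** Amend the withdrawal sections, Visit 1, Study Outcome Measurements and Ascertainment, and Missing Outcome Data in both the protocol and the SAP:

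1. Keep patients who miss Visit 1 in the study for outcome purposes. Take the index-stump outcome from the adverse-event CRF, the hospital chart and, where consent allows, outside records. Do not rely on the CRF alone, given the bar on targeted questions.
2. Choose one fixed day consistent with the 30-day aim and reconcile the Visit 1 window with it. Count any revision or re-amputation of the index stump up to that day as a healing failure, whatever the new wound looks like. Also count recorded wound breakdown or wound infection, using stated criteria.
3. Report death separately, and as failure in a sensitivity analysis.
4. Keep the index stump's outcome separate from any later participation on the same limb.
5. Replace the not-applicable entry under Missing Outcome Data with this rule.

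The cost is wording in two documents and some chart review, much of it on events already recorded as adverse events. No visit or procedure is added. The downside is that record-based outcomes are coarser than a bedside assessment.

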 23. Kapp, M.B., *Ethical and legal issues in research involving human subjects: do you want a piece of me?* J Clin Pathol, 2006. **59**(4): p. 335-9.
 24. Holdiness, M.R., *Clinical pharmacokinetics of N-acetylcysteine.* Clin Pharmacokinet, 1991. **20**(2): p. 123-34.

STATISTICAL ANALYSIS PLAN

**Protocol Title: N-Acetyl-Cysteine for Healing of
Amputation Stumps in the Setting of Diabetes**

NCT03253328

**Protocol Version 11.0
Date: March 26, 2020**

Statistical Plan

Sample Size Determination and Power

The purpose of this study is to obtain sufficient preliminary data to determine the sample size necessary for a future large definitive clinical trial. For this pilot study, we plan to enroll 25 patients in each group, allowing for a dropout rate of 10% per group.

We emphasize that effect size (the expected difference in primary outcome between the treatment and control groups) should not be determined by the pilot study. Rather it is determined by the minimum clinically important difference. However, the effect size from the pilot give us some ideas about possible achievable difference.

Interim Monitoring and Early Stopping

An interim analysis will be conducted once >30 patients are enrolled in the study. Analysis will focus on determining differences between NAC and control group. Interim analysis will help determine early differences between the study groups and safety profile of study intervention. The investigators may end the study early depending on study findings, safety profile of the data, and/or if data is adequate for a peer-reviewed publication.

Analysis Plan

Data analysis include (1) the partition of variation of outcome measurements into within and between patient components to obtain standard deviation of measurements, intra-class correlation of the measurements, (2) use of appropriate regression model (GEE or mixed effect regression) to compare the outcome measurements between two groups, while accounting for the intra-class correlation. Interpretation of analysis should be made within the context of a pilot study where we have a pre-specified hypothesis but do not have power analysis for testing the hypothesis.

Statistical Methods

One of the main study outcomes (and in the future large study) is the stump perfusion assessment, which is a continuous variable measured three times (D0, D3, and D5) after treatment. Based on this longitudinal repeated measurement study design, the preliminary data needed for designing future study include: (1) variance of single measurement, (2) covariance (correlation) among the repeated measurements over time within an individual, (3) level of outcome measurements in patients with and without the treatment.

Missing Outcome Data

Not applicable

Unblinding Procedures

The BJH Investigational Pharmacy will maintain a record of each patient's medical record number and to which arm of the study they were assigned. No member of the vascular surgery investigational team will have access to this information. This will serve to maintain blinding and reduce any unwanted during the trial and subsequent analysis of collected data. Un-blinding of patient data will occur during the interim analysis, and at the end of the study. For un-blinding the pharmacy will then un-blind the study to the investigators such that appropriate conclusions can be made regarding the efficacy of the investigational agent.
